### STATISTICAL METHODS

**Sample size:** A sample size of 565 subjects randomized using a 95:95:95:140:140 ratio to receive either 30, 60 mg, 120 mg, or 300 mg MEDI3506 or matching placebo will give approximately 85:85:85:125:125 evaluable subjects per group. This will provide at least 85% power for the 300 mg arm and 80% power for the 30, 60, and 120 mg arms to detect a 30% reduction in change from baseline to Day 169 (Week 24) in UACR between each MEDI3506 treatment group and placebo group (or placebo/MEDI3506 ratio of 1.429) with a one-sided alpha of 0.05 without multiplicity adjustment, assuming a coefficient of variation of 1.31 or standard deviation of 1.0 in log scale.

**Statistical analyses:** The primary efficacy analysis of change from baseline to Day 169 (Week 24) in UACR compared to placebo (on treatment with dapagliflozin as standard of care) will be based on the Per Protocol Population. UACR will be log-transformed and analyzed using mixed model repeated measures (MMRM) method adjusting for fixed categorical effects of treatment, visit, and treatment-by-visit interaction, randomization stratification factors, and the continuous covariates of baseline log UACR and baseline log UACR-by-visit interaction. An unstructured covariance structure may be used to model the within-subject errors. The primary efficacy endpoint will also be analyzed using an analysis of covariance adjusting for treatment, randomization stratification factors, and baseline log UACR with last-observation-carried-forward (LOCF) imputation for missing post-baseline measurements.

The secondary efficacy analysis of change from baseline to Day 85 (Week 12) in UACR and change from Day 85 (Week 12) to Day 169 (Week 24) in UACR will be analyzed similarly to that of the primary efficacy analysis and be based on the Full Analysis Population and Per Protocol Population, respectively. For the proportions of subjects with  $> 30\%$ ,  $> 40\%$ , and  $> 50\%$  reduction in UACR, logistic regression models will be used, adjusting for treatment, randomization stratification factors, and baseline albuminuria status based on the Full Analysis Population and the Per Protocol Population.

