### 3.1.2 Treatment Regimen

CCI

- Group 1: MEDI3506 30 mg (0.2 mL), n = 95
- Group 2: MEDI3506 60 mg (0.4 mL), n = 95
- Group 3: MEDI3506 120 mg (0.8 mL), n = 95
- Group 4: MEDI3506 300 mg (2 mL), n = 140
- Group 5: Placebo (0.2 mL), n = 32
- Group 6: Placebo (0.4 mL), n = 32
- Group 7: Placebo (0.8 mL), n = 32
- Group 8: Placebo (2 mL), n = 44

All subjects will also receive daily oral tablets of 10 mg dapagliflozin starting on Day 85 until Day 168. Subjects already taking an SGLT2i will be rolled over to 10 mg dapagliflozin.

Dapagliflozin should be taken in the morning with or without food.

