**Table 6 Schedule of Treatment Period Study Procedures**

Study Period	Treatment Period							Early D/c Visit
Visit Number	V3	V4	V5	V6	V7	V8	V9	
Procedure / Study Day	Day 1	Day 29 (± 5 days)	Day 57 (± 5 days)	Day 85 (± 5 days)	Day 113 (± 5 days)	Day 141 (± 5 days)	Day 169 (± 5 days)	

- a Including focused cardiac exam (Section 4.3.2.2).
- b For the first 2 doses of MEDI3506 or placebo, patients are to remain at the site for  $\geq 2$  hours or until stable, whichever is later. In addition, vital signs will be taken before and immediately after administration of MEDI3506 or placebo, and at 30 minutes ( $\pm 5$  minutes) as well as 120 minutes ( $\pm 10$  minutes) thereafter or until stable, whichever is later. Following the observation period, subject discharge will be at the discretion of the investigator. For all other dosing visits, vital signs will be collected 30 minutes ( $\pm 5$  minutes) after administration of MEDI3506 or placebo or when stable.
- c May be performed independently of other Visit 9 procedures within the visit window.
- d PK samples on MEDI3506/placebo dosing days will be collected pre-dose of MEDI3506/placebo administration.
- e Dapagliflozin PK samples will be collected at the following time points relative to dapagliflozin administration: Day 141 (predose and 2 h postdose) and Day 169 on study visit. Patients will be reminded to take dapagliflozin on site visits during dapagliflozin administration time (Day 85 to Day 168/Visit 6 to Visit 8).

- g If consent obtained.
- h After randomization. If, for any reason, the sample is not drawn pre-dose on Visit 3 (Day 1), it may be taken at any visit until the final follow-up visit/Early Discontinuation Visit.
- i Subjects collect 3 consecutive first morning void midstream urine samples (ideally day of visit and preceding 2 days [refrigerated overnight]) which are returned on the day of visit.
- j In the event that a dose cannot be administered within the window of the scheduled dosing date, the dose may be administered outside of the dosing window as long as it is at least 14 days prior to the next dose and recorded as a protocol deviation.
- k Subjects enrolled that have reached the Day 85 visit prior to Amendment 2 approval should continue in the study without the addition of dapagliflozin to their dosing regimen.

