**Table 11 Study Populations**

Population	Description
Enrolled	All subjects who sign the informed consent form.
Full Analysis Population	All subjects who are randomized and receive any study drug. Subjects are evaluated according to the treatment assigned at randomization. The Full Analysis Population will be used for all analyses of demographic baseline characteristics and efficacy data.
Per Protocol Population	A subset of the Full Analysis Population consisting of all subjects who receive the additional treatment with dapagliflozin post Week 12 and do not violate the terms of the protocol in a way that may affect the primary efficacy endpoint significantly. All decisions to exclude subjects from the per protocol analysis set will be made and documented prior to the unblinding of the study.
Safety Analysis Population	All subjects who are randomized and receive any study drug. Subjects are evaluated according to the actual treatment they received. The Safety Analysis set will be used for all safety analyses.
PK Population	All subjects in the Full Analysis Population who have at least one detectable MEDI3506 serum concentration measurement posttreatment. The PK Analysis set will be used for all PK analyses.

PK = pharmacokinetic(s).

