## 4.8.3 Efficacy

### 4.8.3.1 Primary Efficacy Analysis

The primary efficacy endpoint for this study is change from baseline to Day 169 (Week 24) in UACR compared to placebo and will be analyzed based on the Per Protocol Population. For the intercurrent events, if a subject is lost to follow-up, discontinues treatment due to AE or lack of efficacy, or uses prohibited medication, the UACR data are treated as missing after the event and no imputation is performed. As UACR is assumed to follow a log-normal

distribution, it will be log-transformed for statistical analysis purposes. The primary analysis will use a mixed model repeated measures (MMRM) analysis of change from baseline in UACR without multiplicity adjustment. The model will adjust for fixed categorical effects of treatment, visit, and treatment-by-visit interaction, randomization stratification factors, and the continuous covariates of baseline log UACR and baseline log UACR-by-visit interaction. UACR will be log-transformed before entering the data in the MMRM analysis to alleviate the skewness of the data. Randomization stratification factors are with SGLT2i background or not, in Japan or rest of world.

To allow generality for the covariance structure for the repeated measures, the variance-covariance matrix will be assumed to be unstructured ie, purely data dependent. If the unstructured variance-covariance matrix will not fit, then suitable alternatives will be considered with details provided in the SAP. In this MMRM model, all subjects and all data points will be included. No subjects will be excluded because of missing data, and no imputation will be done for missing data. Additionally, there will be no adjustment for multiplicity.

Additionally, the primary efficacy endpoint will also be analyzed using an analysis of covariance adjusting for treatment, randomization stratification factors, and baseline log UACR with last-observation-carried-forward (LOCF) imputation for missing postbaseline measurements.

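### The supportive LOCF ANCOVA of the Week 24 endpoint can carry a UACR value from before dapagliflozin forward as the on-dapagliflozin result

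*Protocol*

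**What the plan says.** **Analyses of the primary endpoint.** Section 4.8.3.1 makes an MMRM of log UACR primary, without imputation. It then adds an ANCOVA adjusting for treatment, stratification factors and "baseline log UACR with last-observation-carried-forward (LOCF) imputation for missing postbaseline measurements". The Synopsis repeats this: "with last-observation-carried-forward (LOCF) imputation for missing post-baseline measurements". Neither place says which visits may be carried forward.

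**What the endpoint measures.** The Synopsis describes the Week 24 comparison as "compared to placebo (on treatment with dapagliflozin as standard of care) will be based on the Per Protocol Population".

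**Regimen.** Section 3.1.2: "All subjects will also receive daily oral tablets of 10 mg dapagliflozin starting on Day 85 until Day 168". Section 4.6.1 has the tablets allocated at Visit 6, which is the Day 85 visit. Section 1.8.2 hypothesises that dapagliflozin lowers albuminuria further.

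**Urine timing.** The UACR footnote to Table 6 asks for three consecutive first-morning samples, ideally from the visit day and the two days before.

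**Population.** Table 11 defines the Per Protocol Population as "all subjects who receive the additional treatment with dapagliflozin post Week 12 and do not violate the terms of the protocol". Only violations that could matter materially for the primary endpoint count.

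**Data after an intercurrent event.** After loss to follow-up, stopping treatment for an adverse event or lack of efficacy, or use of prohibited medication, Section 4.8.3.1 says that "the UACR data are treated as missing after the event and no imputation is performed".

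**The concern.** LOCF assumes that a subject's last value can stand in for the value at the endpoint. Here the background regimen changes by design halfway through, and the protocol expects that change to lower UACR. The tablets are handed out at the Day 85 visit, while the urine for that visit was passed the same morning and on the two mornings before. The Day 85 value is therefore essentially pre-dapagliflozin, and the first on-dapagliflozin value is at Day 113.

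Requiring dapagliflozin after Week 12 keeps earlier dropouts out of the Per Protocol Population. It does not remove a subject who starts dapagliflozin and then has no usable UACR at Day 113, 141 or 169. The ANCOVA as written gives that subject a Week 24 result from the earlier regimen.

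At stake is the meaning of the supportive analysis. Agreement or disagreement with the MMRM could partly reflect when subjects left rather than what MEDI3506 did. Section 4.8.3.2 also analyses the Day 85 to Day 169 change in a similar way. If LOCF is included there, a carried Day 85 value forces a change of exactly zero.

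**Working it through.** **1. The plan's own figures.** Section 4.8.2 assumes a log-scale SD of 1.0, a 30% reduction, one-sided alpha 0.05, and 85 or 125 evaluable subjects against 125 on placebo.
- Effect: ln(1/0.7) = 0.357. CV: sqrt(e - 1) = 1.311, which matches the stated 1.31.
- 85 vs 125: SE = sqrt(1/85 + 1/125) = 0.141; power 81.4% (stated 80%).
- 125 vs 125: power 88.0% (stated at least 85%).

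These figures stand and are not in dispute.

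**2. Bias of the LOCF contrast.** Let qA and qP be the fractions of the active and placebo arms whose Week 24 value is a carried Day 85 value. Let g be the log reduction due to dapagliflozin, and m85 and m24 the log reductions due to MEDI3506 at Day 85 and Week 24. Relative to Day 85 on placebo:
- Active mean = (1 - qA)(-g - m24) + qA(-m85)
- Placebo mean = (1 - qP)(-g)
- Difference = -m24 + **(qA - qP)g + qA(m24 - m85)**

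The bold part is the bias. It is zero if qA = qP and m85 = m24. With m85 = m24, more carrying on active understates MEDI3506, and more carrying on placebo overstates it.

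**3. Size when the fractions differ (m85 = m24).** The documents give no size for the dapagliflozin effect, so 20-35% is an assumption: g = -ln(0.80) = 0.223 to -ln(0.65) = 0.431. A difference of 2-4 percentage points is also an assumption.

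| qA - qP | g = 0.223 | g = 0.431 |
|---|---|---|
| 0.02 | 0.0045 (0.4%) | 0.0086 (0.9%) |
| 0.04 | 0.0089 (0.9%) | 0.0172 (1.7%) |

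A true ratio of 0.70 would appear as about 0.703 to 0.712. With the imbalance reversed it would appear as about 0.697 to 0.688. The largest shift is 0.0172/0.141 = 0.12 of the standard error of the 85 vs 125 comparison.

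**4. Size when the MEDI3506 effect differs.** With 5% carried in both arms and half the effect at Day 85 (assumptions), the bias is 0.05 x 0.178 = 0.009. The ratio becomes 0.706, a 29.4% reduction instead of 30%.

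**5. Plausibility of the fractions.** The only attrition figure is 505 evaluable of 565, so 1 - 505/565 = 10.6% not evaluable. Spread evenly over the six 4-week intervals (assumption), that is about 1.8% for Day 85 to Day 113, the interval that matters. A 2-4 point difference between arms is already generous against this.

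**6. Arm-level change.** Even with a balanced contrast, carrying 5% raises the placebo arm's Week 24 geometric mean by 1.1% (0.05 x 0.223) to 2.2% (0.05 x 0.431).

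**The case against.** The strongest reply is that little depends on this analysis and that few subjects are exposed. Most of that stands.

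- **It is not the primary analysis.** The ANCOVA is additional and no success rule is attached to it. A reader might infer that the primary result is biased; it is not, because the MMRM imputes nothing.
- **Dropouts before Day 85 are not shown to be affected.** A reader might infer that they are, because Table 11 also states that "The Full Analysis Population will be used for all analyses of demographic baseline characteristics and efficacy data". But Section 4.8.3.1 assigns the primary endpoint to the Per Protocol Population, and the ANCOVA is of that endpoint. The Table 11 sentence is a separate inconsistency.
- **A later UACR is often collected.** Subjects who stop MEDI3506 during the dapagliflozin period attend an Early Discontinuation Visit with UACR (Section 4.1.6, Table 6), and those who stop only dapagliflozin continue their visits. This narrows the problem without closing it. Subjects lost to follow-up have no such value. If the missing-after-event rule also governs the ANCOVA, which the section does not say, that value is discarded for those stopping for an adverse event or lack of efficacy.
- **Not every carried value is wrong by the full dapagliflozin effect.** Subjects with SGLT2i background are switched at Day 85 (Section 4.1.2, criterion 7), so their earlier values already reflect an SGLT2i. If half of the carried subjects were such subjects, and switching left UACR unchanged (both assumptions), the range in step 3 would halve.
- **Two further criticisms are not supported.** That the LOCF standard error is too small is not shown here. That informative dropout goes untested cannot be concluded, because Section 4.8.3.5 leaves other sensitivity analyses to the SAP, which is not at hand.

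What remains is that the protocol fixes an imputation rule which, followed literally, carries values across a planned change of regimen.

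**Conclusion.** The point holds for the supportive analysis only. The LOCF ANCOVA has no limit on the visit carried, so a Per Protocol subject with no usable UACR from Day 113 on contributes a pre-dapagliflozin value as the Week 24 on-dapagliflozin result.

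Bias in the contrast needs unequal carried fractions or a MEDI3506 effect that changes across Day 85, and it can run in either direction. With a 20-35% dapagliflozin effect, a 2-4 point difference in carried fractions and a constant MEDI3506 effect, the ratio shifts by about 0.4-1.7%. All three are assumptions. A reader might infer a larger bias by supposing 10 points or more of imbalance, but that is close to the plan's entire allowance of 10.6% for non-evaluable subjects.

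This does not threaten the primary result or the sample size. It is worth correcting because the rule is stated, does not suit this design and is cheap to replace.

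**What to change.** By protocol amendment, or by a documented SAP change before unblinding, do one of the following:

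1. Drop the LOCF ANCOVA from the Synopsis and Section 4.8.3.1.
2. Replace it with ANCOVA after multiple imputation in the Per Protocol Population. Earlier values may serve as predictors, but no pre-dapagliflozin value may stand as the Week 24 result. The rule should cover every reason in Section 4.8.3.1: for example, imputation from the placebo arm's post-Day-85 values for subjects who stop for an adverse event or lack of efficacy, and missing-at-random imputation for loss to follow-up and prohibited medication.

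Under option 2, also state whether the missing-after-event rule applies to this analysis. In either case, state that LOCF is not used for the Day 85 to Day 169 change.

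The cost is a little more programming and the documentation of the change. Visits, subjects and sample size stay as they are. Placebo-based imputation addresses a somewhat different question from the MMRM, so the supportive estimate may be somewhat smaller and should be labelled accordingly.

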#### **4.8.3.2 Secondary Efficacy Analysis**

The change from baseline to Day 85 (Week 12) in UACR will be analyzed similarly to that of the primary efficacy endpoint based on the Full Analysis Population. Change from Day 85 (Week 12) to Day 169 (Week 24) in UACR will be analyzed similarly to that of the primary efficacy endpoint based on the Per Protocol Population. For the proportions of patients with > 30%, > 40%, and > 50% reduction in UACR, logistic regression models will be used adjusting for treatment, randomization stratification factors, and baseline albuminuria status based on the Full Analysis Population and the Per Protocol Population.

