### 1.8.2 Secondary Hypotheses

MEDI3506 will reduce albuminuria compared with placebo on top of standard of care, including ACEi or ARB, and will exhibit an acceptable safety, immunogenicity, and PK profile in subjects with DKD. Dapagliflozin on top of MEDI3506 will further reduce albuminuria.

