**Table 2 Secondary Objectives and Associated Endpoints**

Type	Objective	Endpoint
		
 
• BNP
 
• Laboratory assessments (hematology, clinical chemistry, and urinalysis)
 
• For subjects testing positive for COVID-19 during the intervention and follow-up periods, the number and proportion of subjects with AEs/SAEs, as well as the number and proportion of subjects with COVID-19 AEs/SAEs, and the proportion of asymptomatic subjects.
 

PK, Immunogenicity	To describe the PK and immunogenicity of MEDI3506 in subjects with DKD	MEDI3506 serum concentrations and ADA incidence occurring throughout the study
Efficacy	To evaluate the effect of MEDI3506 in combination with ACEi or ARB with and without dapagliflozin on albuminuria in subjects with DKD	
 
• Proportion of subjects with > 30% reduction in UACR at Day 169 (Week 24)
 
• Proportion of subjects with > 40% reduction in UACR at Day 169 (Week 24)
 
• Proportion of subjects with > 50% reduction in UACR at Day 169 (Week 24)
 
• Change from baseline to Day 85 (Week 12) in UACR
 
• Change from Day 85 (Week 12) to Day 169 (Week 24) in UACR
 

ACEi = angiotensin converting enzyme inhibitors; ADA = anti-drug antibody; AE(s) = adverse event(s); ARB = angiotensin receptor blockers; BNP = B-type natriuretic peptide; ECG = electrocardiogram; EOS = end of study; DBP = diastolic blood pressure; DKD = Diabetic Kidney Disease; LVEF = left ventricular ejection fraction; PK = pharmacokinetic; SAE(s) = serious adverse event(s); SBP = systolic blood pressure; TEAE(s) = treatment emergent adverse event(s); TESAE(s) = treatment emergent serious adverse event(s); UACR = urine albumin to creatinine ratio

CCI

CCI

CCI

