### 3 STUDY DESIGN

#### 3.1 Description of the Study

##### 3.1.1 Overview

This is a Phase 2b, randomized, double-blind, placebo-controlled, multicenter study to evaluate the efficacy, safety, PK, and immunogenicity of MEDI3506 in adult subjects with DKD; defined as subjects with T2DM and an eGFR of 25-75 mL/min/1.73 m^2 with a urine albumin:creatinine ratio (UACR) in the range of 100-3000 mg/g, who meet all eligibility criteria. Furthermore, the additive effect of the SGLT2i dapagliflozin taken together with MEDI3506 on albuminuria will be assessed for 12 weeks when subjects will be treated with MEDI3506/placebo and dapagliflozin. Subjects who have started on the Phase 2a study prior to Amendment 2 will be transitioned to the Phase 2b and given dapagliflozin starting on Day 85 (Week 12). Subjects who have completed 12 weeks of treatment prior to implementation of Amendment 2 will continue on treatment with MEDI3506/placebo without dapagliflozin.

Approximately 565 subjects, from around 130 study sites among multiple countries will be randomized (95:95:95:140:140) to MEDI3506 30, 60, 120, or 300 mg, or volume-matched placebo. Note that the 19 subjects who were enrolled and discontinued prior to the study hold on 24 March 2020 due to COVID-19 are not included in the total count of 565 subjects.

[figure not shown]
Subjects will be dosed subcutaneously CCI

Following the signing of informed consent, subjects will be assessed for study eligibility during a screening period of up to 35 days (Day -37 to Day -3) followed by a 168-day (24-week) treatment period and a 70-day (10-week) follow-up period (Figure 1).

**Figure 1** Study Flow Diagram

ACEi = angiotensin converting enzyme inhibitor; ARB = angiotensin receptor blocker; eGFR = estimated glomerular filtration rate in mL/min/1.73m^2; Q4W = every 4 weeks; QD = once daily; T2DM = type 2 diabetes mellitus; UACR = urine albumin to creatinine ratio in mg/g.

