### **4.6 Treatment Assignment and Blinding**

#### **4.6.1 Methods for Assigning Treatment Groups**

An IXRS will be used for randomization to a treatment group and assignment of blinded investigational product kit numbers. A subject is considered randomized into the study when the investigator notifies the IXRS that the subject meets eligibility criteria and the IXRS provides the assignment of blinded investigational product kit numbers to the subject.

Subjects will be stratified at the time of randomization in order to ensure approximate balance between treatment groups within each sub-population.

- Stratum 1: Subjects without SGLT2i background outside Japan
- Stratum 2: Subjects with SGLT2i background outside Japan
- Stratum 3: Subjects without SGLT2i background in Japan
- Stratum 4: Subjects with SGLT2i background in Japan

Subjects will be randomized to receive 30, 60, 120, or 300 mg MEDI3506 (95, 95, 95, and 140 subjects, respectively) CCI placebo (32, 32, 32, and 44 subjects, respectively) by an IXRS system.

IXRS will also allocate 2 bottles of dapagliflozin (35 tablets each) at Visit 6 and 1 bottle of dapagliflozin (35 tablets) at Visit 7 to eligible subjects that will be used to cover the need of daily administration between two visits of MEDI3506/placebo administration. This will ensure that the patient has sufficient stock of dapagliflozin if a visit is delayed. If there is any issue with one of the bottles (eg, lost or damaged), the patient can receive a replacement at any visit (Visit 7 or Visit 8); kit replacement option is available in IXRS.

The procedure for using IXRS is as follows:

- The investigator or designee contacts the IXRS and provides the SID number and subject's baseline characteristic(s) used to verify that it is the same subject
- The correct amount of kits of MEDI3506 and/or placebo will be assigned to the subject
- Confirmation of kit assignment is sent to the unblinded investigational product manager who prepares the investigational product to be dispensed to the subject per the response system and records the appropriate information in the investigational product accountability log
- Blinded study personnel will receive a notification containing a dose tracking number, that will not disclose how many kits are assigned to the subject.

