#### **4.7.3 Considerations for SGLT2i and RAASi**

If a subject is on SGLT2i treatment prior to enrollment into this study, they must have been on a stable dose for at least 4 weeks prior to the randomization visit. Starting additional SGLT2i therapy during the study, before Day 169/Early Discontinuation Visit, is not permitted. Any existing SGLT2i treatment will be discontinued on Day 85. All subjects will receive 10 mg

dapagliflozin by mouth daily starting on Day 85 until Day 168. Starting additional SGLT2i therapy at or after Day 169/Early Discontinuation Visit is permitted.

In general, any dose changes of SGLT2i treatment should be avoided during the study unless due to medical necessity. If the subject needs to interrupt SGLT2i treatment for any reason, they should be allowed to re-start it again once the respective medical condition gets resolved.

Subjects who have started on the Phase 2a study prior to Amendment 2 will be transitioned to the Phase 2b and given 10 mg dapagliflozin starting on Day 85 (Week 12). Any existing SGLT2i treatment will be discontinued. Subjects who have completed 12 weeks of treatment prior to approval of Amendment 2 will continue on treatment with MEDI3506/placebo without dapagliflozin.

For patients with T2DM and albuminuria, clinical guidelines recommend treatment with ACEi or ARB and SGLT2i (dapagliflozin in this study) (de Boer et al, 2020). The recommendation of treating patients with T2DM, CKD, and an eGFR > 30 ml/min per 1.73 m^2 with an SGLT2i and RAASi is based on the highest level of evidence (1A) that these therapies are safe and efficient in reducing adverse kidney events.

Once daily 10 mg dapagliflozin has been studied in large cardiovascular and renal outcomes studies on top of standard of care, including ACEi or ARB (DAPA-HF and DAPA-CKD studies) (Heerspink et al, 2020b; McMurray et al, 2019). Among patients with CKD and T2DM, the risk of a composite of a sustained decline in eGFR of at least 50%, end-stage kidney disease, or death from renal or cardiovascular causes was significantly lower with dapagliflozin than with placebo. Hence, discontinuation of ACEi or ARB or dapagliflozin should be avoided. Permanent discontinuation should be regarded as a last resort.

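### The Day 85 to Day 169 comparison with placebo does not test the secondary hypothesis that dapagliflozin added to MEDI3506 lowers albuminuria further

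*Protocol*

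**What the plan says.** **Aim.** The Synopsis and section 1.8.2 state the hypothesis "Dapagliflozin on top of MEDI3506 will further reduce albuminuria". Section 3.1.1 repeats it as a design aim: "the additive effect of the SGLT2i dapagliflozin taken together with MEDI3506 on albuminuria will be assessed for 12 weeks".

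**Endpoint.** Table 2 lists "Change from Day 85 (Week 12) to Day 169 (Week 24) in UACR" and names no comparator.

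**Analysis.** Section 4.8.3.2 says "Change from Day 85 (Week 12) to Day 169 (Week 24) in UACR will be analyzed similarly to that of the primary efficacy endpoint", in the Per Protocol Population. Section 4.8.3.1 defines the model being copied: "The primary efficacy endpoint for this study is change from baseline to Day 169 (Week 24) in UACR compared to placebo". It is an MMRM with treatment, visit, treatment-by-visit, the stratification factors, baseline log UACR and its interaction with visit. It has no term for SGLT2 inhibitor background by visit or by treatment.

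**Treatment.** Under 3.1.2 all subjects take dapagliflozin from Day 85 to Day 168. For those already on another drug of the class, 4.7.3 says "Any existing SGLT2i treatment will be discontinued on Day 85", and dapagliflozin replaces it. These subjects are randomised in their own strata, for example "Stratum 2: Subjects with SGLT2i background outside Japan" (4.6.1), with no stated share or cap. The Per Protocol definition in Table 11 does not exclude them.

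**The concern.** The hypothesis is about what dapagliflozin does in people already receiving MEDI3506. The specified analysis is about how MEDI3506 differs from placebo. When both sides of the comparison start dapagliflozin on the same day, the second question carries no information on the shared part of the first.

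What is at stake is interpretation. A contrast near zero could be taken as showing that dapagliflozin adds nothing. A contrast favouring MEDI3506 could be taken as showing that it adds something. Neither reading would follow. A second, smaller matter is that subjects who swap one SGLT2 inhibitor for another receive no add-on, so they weaken any arm-level estimate of an add-on effect.

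**Working it through.** **1. The plan's own power figure.** Section 4.8.2 gives a 30% reduction, log-scale SD 1.0, one-sided alpha 0.05, and 85:85:85:125:125 evaluable subjects. The log difference is ln(1/0.7) = 0.3567.

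- 300 mg: SE = √(1/125 + 1/125) = 0.1265; 0.3567/0.1265 − 1.645 = 1.175; power 88.0% (stated: at least 85%).
- 30, 60 and 120 mg: SE = √(1/85 + 1/125) = 0.1406; 0.3567/0.1406 − 1.645 = 0.892; power 81.4% (stated: 80%).

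Both stated figures hold. They concern the primary endpoint; no power is stated for the Day 85 to Day 169 change.

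**2. What each quantity estimates.** For the log change from Day 85 to Day 169, let t be drift over time, d the dapagliflozin effect common to the arms, i the MEDI3506-by-dapagliflozin interaction, and l any further MEDI3506 effect after Week 12 (MEDI3506/placebo dosing continues at Visits 6 to 8, Table 6).

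| Quantity | Content |
|---|---|
| Change in a MEDI3506 arm | t + d + i + l |
| Change in the placebo arm | t + d |
| MEDI3506 minus placebo | i + l |
| Hypothesis in 1.8.2 | d + i |

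The contrast does not contain d. It is zero only if both i and l are zero. The within-arm change contains d, but also t and l.

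**3. Size of the loss.** Assumptions not in the protocol: SD 1.0 for this change, i = l = t = 0, and a dapagliflozin reduction of 20%, 30% or 40% in every arm. In 100,000 simulated trials per case, with 85 or 125 on MEDI3506 against 125 on placebo, the mean contrast ratio is 1.00 and the one-sided rejection rate is about 5%, which is alpha. At n = 85 a one-sample calculation on the within-arm change gives 0.66, 0.95 and 0.999 for the same three effects. The signal is thus removed by the subtraction and not by the sample size. Those three figures are not a case for a within-arm test, because t and l are confounded with d.

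**4. Switchers.** Assume a reduction e in subjects without SGLT2 inhibitor background, none from a switch, and a share s of switchers. The pooled geometric reduction is 1 − (1 − e)^(1 − s). With e = 30%:

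- s = 20%: 1 − 0.7^0.8 = 24.8%
- s = 30%: 1 − 0.7^0.7 = 22.1%
- s = 50%: 1 − 0.7^0.5 = 16.3%

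This describes a within-arm change, not the planned placebo contrast. The protocol gives neither e nor s.

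**The case against.** The best defence is that the objective in Table 2 is about the effect of MEDI3506 with and without dapagliflozin. Sections 1.6 and 3.2.3 present the aim as learning how MEDI3506 interacts with standard care. The randomised placebo comparisons at Day 85 and Day 169, and the difference in change between those days, are natural estimates for that purpose. This stands. A reader might infer that the objective goes unanswered at both time points; the text does not support that.

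Second, the placebo comparator for this endpoint is inferred. Table 2 names none, the same MMRM yields arm-level means, and 4.8.1 leaves further detail to the SAP. This stands in part. The protocol nevertheless fixes the population and points to an analysis whose contrast is against placebo. It nowhere names a within-arm quantity as the answer to the hypothesis.

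Third, pooling might seem to spoil the Week 12 analysis, for which 4.8.3.2 says "The change from baseline to Day 85 (Week 12) in UACR will be analyzed similarly to that of the primary efficacy endpoint". Section 1.6 does describe the first period loosely, as MEDI3506 or placebo with ACEi or ARB. But the hypothesis speaks of standard of care that includes those drugs, and the objective says without dapagliflozin, not without the class. Background SGLT2 inhibitor use is admitted (4.1.2), stratified (4.6.1) and adjusted for (4.8.3.1). The pooled Week 12 comparison is valid.

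Finally, a within-arm change cannot isolate dapagliflozin. No arm is randomised to go without it, and those who passed Week 12 before Amendment 2 were not randomised to that and fall outside the Per Protocol set. This is right, and it limits the repair.

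**Conclusion.** The point holds in a narrow form. The dapagliflozin hypothesis in the Synopsis and 1.8.2, echoed in 3.1.1, is not tested by the analysis in 4.8.3.2 as read with 4.8.3.1. The contrast estimates i + l, while the hypothesis is about d + i.

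It would be too strong to say that the contrast must be zero. That needs both no interaction and no later MEDI3506 effect, and the protocol asserts neither. The dilution figures are illustrations that rest on an assumed 30% effect, no effect of a switch, and assumed shares.

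This concerns one secondary hypothesis in a Phase 2b trial without multiplicity adjustment. It should be corrected because the result is otherwise easy to misread.

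**What to change.** In 4.8.3.2 and 1.8.2, with the Synopsis and 3.1.1 aligned:

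1. State that the MEDI3506-placebo difference in the Day 85 to Day 169 change estimates interaction plus any later MEDI3506 effect, and is not evidence for or against a dapagliflozin effect.
2. Then choose one of two routes. Either reword the hypothesis as that interaction, or address it with the within-arm least-squares mean change from Day 85 to Day 169 in each MEDI3506 arm, in strata 1 and 3 (no SGLT2 inhibitor background), from a model with a background-by-visit term. Label the second route descriptive and uncontrolled, since it is confounded with time and continued MEDI3506 exposure.
3. Optionally, show the Week 12 MEDI3506-placebo comparison in strata 1 and 3 beside the pooled one.

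The cost is wording and a few extra estimates, from strata already randomised and data already collected. The downside is precision: restricting to strata 1 and 3 multiplies the standard error by about 1/√(1 − s), that is 1.12, 1.20 or 1.41 if 20%, 30% or 50% are on background treatment.
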